5.1.5 Maintenance Therapy

Maintenance therapy should start 4 weeks after completion of adjuvant therapy.

- Patients in the control arm (Arm A) will receive nivolumab alone on Day 1 of every 4 week cycle for up to 24 cycles (Cycles 13-36).
- Patients in the experimental arm (Arm B) will receive nivolumab on Day 1 of every 4 week cycle for up to 24 cycles (Cycles 13-36) and FVP-CV301 will be given concomitant every twelve weeks (every 3 cycles) for 8 doses.

Post-therapy patients will be under surveillance per NCCN guidelines with repeat CEA every 3 months for 2 years followed by every 6 months for 1 year (total 3 years), repeat CT of the C/A/P every 3 months for 2 years followed by every 6 months for up to 1 year (total 3 years), and colonoscopy at one year with repetition based on findings at the time of the procedure.

In the event of recurrence, the patient's disease and next line of therapy will be managed according to the individual cancer center's disease group management team. If the recurrence is within two years, the patient will continue to receive their scheduled nivolumab ± vaccine. In the event that administration of nivolumab ± vaccine is impacting the delivery or tolerability of standard of care next line therapy, patients will be removed from protocol therapy but will continue to be followed on study.

5.2 mFOLFOX6

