6. TOXICITIES AND DOSE DELAYS/DOSE MODIFICATIONS

Guidelines for dose delays and dose modifications are described below, and applicable to the start of each cycle as well as during the cycle if treatment-related toxicities occur. Subjects enrolled in this study will be evaluated clinically and with standard laboratory tests before and at regular intervals during their participation in this study as specified in Study Calendar & Evaluations. The NCI Common Terminology Criteria for Adverse Events (CTCAE) v4 will be used to grade adverse events. Subjects will be evaluated for adverse events (all grades), serious adverse events, and adverse events requiring study drug interruption or discontinuation as specified in Study Calendar & Evaluations.

Dose modifications are always based on the dose used in the previous cycle.

The investigator may attribute each toxicity event to the vaccine, nivolumab, mFOLFOX6, or any component of the combination therapy. Reduction or holding of one agent and not the other agent is appropriate if, in the opinion of the investigator, the toxicity is related to one of the study drugs. For example, if mFOLFOX6 is held due to an AE attributed to that component or the combination, then the vaccine and/or Nivolumab may continue to be administered. The drug to which the investigator is attributing the AE must be documented. If there is more than a 2-day delay for any reason, administration of study drugs should be re-aligned so that the chemotherapy falls within +2 days with the next cycle.

6.1 mFOLFOX6

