11. Detailed description of study treatment can be found in Section 5. Beginning 4 weeks after completion of adjuvant therapy, patients will continue on maintenance nivolumab but on the standard every 4-week schedule +/- vaccination every 12 weeks. A PE, AE assessment, laboratory assessment, and repeat CEA and CA19-9 will be done prior to each treatment. Additionally, participants will undergo re-staging CT C/A/P every 3 months as per current clinical practice standards. Upon completion of treatment, repeat CT of the C/A/P every 3 months for 2 years followed by every 6 months for up to 1 year (total 3 years).

12: Safety Follow Up: The D30 safety follow-up visit should only occur when subjects permanently stop study treatment for whatever reasons (toxicity, progression, or other reason) and should be performed 30 days (+ 7 days) after the last dose of treatment. Subjects who have an ongoing Grade ≥ 2 or serious AE (SAE) at this visit will continue to be monitored by a member of the study team until the event is resolved, stabilized, determined to be irreversible by the site investigator or a new anti-cancer treatment starts, whichever occurs earlier. The D100 safety follow up visit may be done via phone, email or other avenues as appropriate to assess for SAEs.

13: Upon completion of study treatment, patients should be under surveillance per NCCN guidelines with physical exam (PE), AE assessment, laboratory assessment, and repeat CEA every 3 months for 2 years followed by every 6 months for 1 year (total of 3 years). CT C/A/P will be done every 3 months for 2 years, followed by every 6 months for 1 year (total of 3 years). Colonoscopy at one year with repetition based on findings at the time of the procedure. The above are NCCN guidelines but if not followed, do not constitute a deviation from the protocol. Treating staff should monitor according to standard of care for patients receiving immunotherapy medications. If a patient progresses information regarding disease recurrence, anti-cancer treatment and response will be obtained. This may be done via phone call, email or other avenues as appropriate.

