11.2 Reporting

11.2.1 Adverse Events

- AEs will be recorded from time of signed informed consent until 100 days after discontinuation of study drug(s) or until a new anti-cancer treatment starts, whichever occurs first.
- AEs will be recorded regardless of whether or not they are considered related to the study drug(s).
- All AEs will be recorded in the subject's medical record and on the appropriate study specific eCRF form within the EDC system.
- AEs considered related to study drug(s) will be followed until resolution to \leq Grade 1 or baseline, deemed clinically insignificant, and/or until a new anti-cancer treatment starts, whichever occurs first.

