11.2.2 Serious Adverse Events (SAEs)

11.2.2.1 Site Requirements for Reporting SAEs to HCRN

- SAEs will be reported from time of signed informed consent until 100 days after discontinuation of study drug(s) or until a new anti-cancer treatment starts, whichever occurs first.

- SAEs will be reported on the SAE Submission Form **within 1 business day** of discovery of the event.
- SAEs include events related and unrelated to the study drug(s).
- All SAEs will be recorded in the subject's medical record and on the appropriate study specific eCRF form within The EDC system.
- All SAEs regardless of relation to study drug will be followed until resolution to \leq Grade 1 or baseline and/or deemed clinically insignificant and/or until a new anti-cancer treatment starts, whichever occurs first.

The site will submit the completed SAE Submission Form to HCRN **within 1 business day** of discovery of the event. The form may be submitted to HCRN electronically to [contact]. The site investigator is responsible for informing the IRB and/or other local regulatory bodies as per local requirements.

The original copy of the SAE Submission Form and the email correspondence must be kept within the study file at the study site.

Once the SAE has resolved (see resolution guidelines listed in 11.2.2.1), sites must submit a follow-up SAE Submission Form within a reasonable timeframe to HCRN electronically to [contact].

11.2.2.2 HCRN Requirements for Reporting SAEs to Bavarian Nordic and Bristol Myers Squibb (BMS)

HCRN will report all SAEs to Bavarian Nordic (BN) at [contact] and BMS at [contact] **within 1 business day** of receipt of the SAE Submission Form from a site. Follow-up information will be provided to Bavarian Nordic and BMS **within 1 business day** as it is received from site.

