11.3 Sponsor-Investigator Responsibilities

HCRN will send a SAE summary to the sponsor-investigator **within 1 business day** of receipt of SAE Submission Form from a site. The sponsor-investigator will promptly review the SAE summary and assess for expectedness and relatedness.

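### Required AE and SAE reporting stops when a new anti-cancer treatment starts, although section 5.1.5 keeps recurrent patients on nivolumab ± CV301 alongside that treatment

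*Combined protocol and SAP*

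**What the plan says.** **Reporting window.** Section 11.2.1 records AEs from consent until 100 days after "discontinuation of study drug(s) or until a new anti-cancer treatment starts, whichever occurs first". Section 11.2.2.1 has the same limit for SAE reports: 100 "days after discontinuation of study drug(s) or until a new anti-cancer treatment starts, whichever occurs first". Follow-up of events already open can end at the same point. In 11.2.2.1 all SAEs are followed to Grade 1 or "baseline and/or deemed clinically insignificant and/or until a new anti-cancer treatment starts, whichever occurs first", and 11.2.1 has a similar bullet for related AEs.

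**Treatment after recurrence.** Section 5.1.5 leaves next-line therapy to the centre and adds: "If the recurrence is within two years, the patient will continue to receive their scheduled nivolumab ± vaccine". Study drug stops only if giving it "is impacting the delivery or tolerability of standard of care next line therapy, patients will be removed from protocol therapy". Section 5.1.3 follows the same pattern for patients found unresectable. Section 6.4 does not list recurrence as a reason to discontinue.

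**Prohibited medication.** Section 5.7.2 excludes additional anticancer agents while study drugs are being received. Its specific case-by-case allowance is for radiation, and its general release covers only post-treatment follow-up.

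**Onward reporting.** Under 11.2.2.2, HCRN forwards SAEs to both manufacturers within one business day of receiving the site's form. Under 11.3 it sends the sponsor-investigator a summary within one business day "of receipt of SAE Submission Form from a site".

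**The concern.** For a patient still on study drug, the 100-day limb of the window has not begun, so the new-treatment limb decides. A site could follow 11.2 exactly and submit nothing for an SAE that occurs on nivolumab ± CV301 plus next-line therapy. Without the form, the routine route to the manufacturers and the sponsor-investigator is not triggered.

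CV301 is investigational, and section 1.3 reports four subjects given CV301 with nivolumab. Adding an unspecified next-line regimen creates a further combination for which safety data are wanted.

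Separately, 5.7.2 and 5.1.5 cannot both be followed once systemic next-line therapy starts. Section 5.1.5 is the specific text and evidently the intent, so this second point is a wording correction. The reporting cut-off carries the weight.

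**Working it through.** The plan gives no figure to reproduce. The check is a comparison of the rules, followed by the length of exposure they leave uncovered.

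**Rules side by side, for a patient who recurs during maintenance and starts systemic next-line therapy**

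| Rule | Consequence |
|---|---|
| 5.1.5 | Nivolumab ± vaccine continues |
| 11.2.1, 11.2.2.1 | AE recording, SAE reporting and required follow-up close |
| 11.2.2.2, 11.3 | No site form required, so no forwarding by this route |
| 7, footnote 12 | Day-100 contact still due after the last dose, when required reporting has already ended |
| 5.7.2 | Next-line systemic therapy not allowed |

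**Schedule, in weeks from surgery, assuming on-time dosing**

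- Adjuvant start (C5): 6–8 (5.1.4).
- C5 Day 1 to completion of adjuvant therapy: 7 × 2 = 14 to C12 Day 1, or 16 if completion means the end of C12.
- Maintenance starts 4 weeks later (5.1.5). C13 is at 6 + 14 + 4 = 24 at the earliest and 8 + 16 + 4 = 28 at the latest.
- Last scheduled nivolumab (C36): C13 + 23 × 4 = C13 + 92, so week 116–120, or 26.7–27.6 months.
- Maintenance vaccine in Arm B: 8 doses, 12 weeks apart, taking the first at C13.

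**Doses and time left once next-line therapy starts**

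| Start of next-line therapy | Nivolumab doses left (of 24) | Vaccine doses left (of 8) | Weeks to C36 | Plus 100 days |
|---|---|---|---|---|
| Week 52 (12 months) | 16–17 | 5 | 64–68 | 448 + 100 = 548 to 476 + 100 = 576 days, or 18.0–18.9 months |
| Week 104 (24 months) | 3–4 | 1 | 12–16 | 84 + 100 = 184 to 112 + 100 = 212 days, or 6.0–7.0 months |

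Example at week 52: with C13 at week 24, nivolumab falls at weeks 56, 60, …, 116 (16 doses) and vaccine at weeks 60, 72, 84, 96 and 108 (5 doses).

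**How often recurrence might arise (indicative only).** The Figure 1 legend in section 1.1 gives median RFS of 21.9 and 25.7 months in an outside cohort. Assuming exponential RFS, P(event by T) = 1 − exp(−ln 2 × T / median).

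| T (months from surgery) | Median 21.9 | Median 25.7 |
|---|---|---|
| 24 | 0.532 | 0.477 |
| 26.7 | 0.570 | 0.513 |
| 27.6 | 0.583 | 0.525 |

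That is 48–53% by 24 months and 51–58% by the last scheduled dose. Both are shown because 5.1.5 does not say when its two years start. RFS events include deaths and patients who never receive next-line therapy together with study drug, so these are not estimates of the number affected. They show only that the situation is not rare.

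**The case against.** **The clause may be meant only to shorten the 100 days after study drug stops.** Footnote 12 in section 7 points that way: its monitoring of ongoing events begins after permanent discontinuation and can end at a new anti-cancer treatment. This is probably the intent. It is not what 11.2 says, and no exception is made for a patient still being dosed.

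**Safety is still observed.** Section 6 states "Subjects will be evaluated for adverse events (all grades), serious adverse events", the calendar marks AEs at maintenance visits, and footnote 11 requires an AE assessment before each maintenance treatment. Footnote 12 adds: "The D100 safety follow up visit may be done via phone, email or other avenues as appropriate to assess for SAEs". The DSMC reviews data quarterly. All this is true, so the exposure is not unobserved. But none of it resets the 11.2 window, which governs eCRF recording and the one-business-day SAE form.

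**Section 5.7.2 has some give.** Its opening says that discontinuation of trial therapy may be required if a prohibited drug is indicated, and refers questions to the sponsor-investigator. That offers possible discontinuation, which does not reconcile it with continuation under 5.1.5. If 5.7.2 were enforced strictly, study drug would stop at systemic next-line therapy and the reporting gap would not arise there. The two points should therefore not be added together.

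**The size is a ceiling.** Patients may stop earlier for toxicity, by investigator decision or under 5.1.5 itself, and footnote 12 names progression among reasons for stopping. This stands.

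**CV301 has been combined with other checkpoint inhibitors.** Sections 1.3 to 1.3.3 report 8 subjects with pembrolizumab, 37 with atezolizumab and 6 with durvalumab, and describe immune-mediated events as in line with anti-PD-1 alone. This is reassuring context, but it does not replace reporting in this trial.

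**Conclusion.** The concern holds: the reporting rule is wrong as written. Sections 11.2.1 and 11.2.2.1 end required recording, reporting and follow-up at a point where 5.1.5, and 5.1.3 for unresectable patients, still has nivolumab ± CV301 being given.

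The 18–19 months is a maximum for one patient. It assumes next-line therapy at month 12, on-time dosing and study drug continued through C36; with a month-24 start it falls to 6–7 months. The month-12 and month-24 starts are illustrations, not figures from the plan. Neither the primary endpoint nor its analysis is affected. This is a patient-safety correction that should be made, and the 5.7.2 mismatch is a secondary wording point.

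**What to change.** - **11.2.1 and 11.2.2.1, reporting bullets:** continue AE recording and SAE reporting until 100 days after the last dose of any study drug. Let a new anti-cancer treatment close the window only once all study drug has stopped.
- **11.2.1 (related AEs) and 11.2.2.1 (all SAEs), follow-up bullets:** make the same change.
- **5.7.2:** add an exception, worded identically for both arms, for standard next-line therapy under 5.1.5 and for non-protocol standard therapy in unresectable patients under 5.1.3.
- **Alternative:** if the sponsor intends study drug to stop when next-line therapy starts, change 5.1.5 and 5.1.3 instead. That clinical choice is the sponsor's.

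**Cost.** The change is to protocol wording. Reporting runs longer for patients kept on study drug after recurrence, by about 18–19 months in the on-schedule month-12 case. Sites must also attribute events between study drug and next-line therapy.

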11.3 Sponsor-Investigator Responsibilities

HCRN will send a SAE summary to the sponsor-investigator **within 1 business day** of receipt of SAE Submission Form from a site. The sponsor-investigator will promptly review the SAE summary and assess for expectedness and relatedness.

11.4 HCRN Responsibilities to FDA

HCRN will manage the Investigational New Drug Application (IND) associated with this protocol on behalf of the sponsor-investigator. HCRN will cross-reference this submission to Bavarian Nordic's parent IND and BMS's parent IND at the time of submission. Additionally, HCRN will submit a copy of these documents to BN and BMS at the time of submission to FDA.

HCRN will be responsible for all communication with the FDA in accordance with 21CFR312 including but not limited to the 7 and 15 Day Reports, as well as an Annual Progress Report. Additionally, HCRN will submit a copy of these reports to BN and BMS at the time of submission to FDA.

11.5 IND Safety Reports Unrelated to this Trial

BN and BMS will provide to HCRN IND safety reports from external studies that involve the study drug(s) per their guidelines. HCRN will forward safety reports to the sponsor-investigator who will review these reports and determine if revisions are needed to the protocol or consent. HCRN will forward these reports to participating sites **within 1 business day** of receiving the sponsor-investigator's review. Based on the sponsor-investigator's review, applicable changes will be made to the protocol and informed consent document (if required). All IND safety reports will also be made available to sites via the EDC system. Upon receipt from HCRN, site investigators (or designees) are responsible for submitting these safety reports to their respective IRBs, as per their IRB policies.

12. STATISTICAL METHODS

12.1 Study Design

This is a multi-center, 1:1 randomized clinical trial comparing CV-301 vaccine to standard treatment in patients with resectable hepatic metastatic colorectal cancer.

12.2 Objectives and Endpoints

12.2.1 Definition of Primary Objective and Endpoint

Primary objective: We hypothesize that the addition of vaccination with CV301 to Nivolumab and perioperative systemic chemotherapy followed by complete surgical resection in patients with hepatic-limited metastatic colorectal cancer will significantly increase OS as compared to Nivolumab and perioperative systemic chemotherapy followed by surgical resection.

Primary Endpoint: 3-year OS between perioperative mFOLFOX6 plus Nivolumab and CV301 in combination with surgical resection in patients with hepatic-limited metastatic colorectal cancer. For the primary objective OS is defined as the date of metastasectomy to date of death from any cause.

12.2.2 Definition of Secondary Objectives and Endpoints

Recurrence-free survival, best overall response rate by RECIST 1.1 and surgical pathology criteria, proportion of patients amenable to complete resection/ablation upon first recurrence, incidence and severity of perioperative surgical complications as described above. In addition, a comparison of 3-year OS between the two groups as well as a comparison of OS in both groups to historical controls.

Secondary Endpoints: include 3-year recurrence-free survival, best overall response rate by RECIST 1.1 criteria and tumor pathology, perioperative complications and the proportion of patients able to undergo resection/ablation of first recurrences.

12.2.3 Correlative Objectives and Endpoints

Molecular correlates will also be obtained and descriptive statistics applied.

12.3 Sample Size and Accrual

This is a 1:1 randomized clinical trial comparing CV-301 vaccine to standard treatment in patients with resectable hepatic metastatic colorectal cancer. Based on a study by Morse et al. [17], the OS probability at 3 years is 0.588. We would like to detect an increase in OS in the CV-301 study arm with 80% power, using a 2.5% level one-sided log-rank test. This survival analysis will be from the time of metastasectomy.

With a sample size of 70 resected patients (35 per study arm), we will have 80% power to detect an increase in the 3-year OS rate from 58.8% to 88.7% using a 2.5% level one-sided log-rank test. Note that the 3-year survival rate of the vaccine treated cohort in the study by Morse et. al. was 92.5%. We will enroll 74 patients, with the expectation that about 5% of the patients will not go on to resection due to either disease progression or complications of neoadjuvant therapy³, leaving us with approximately 70 resectable patients. If the number of unresectable patients is higher than 5%, then we will enroll up to 78 patients.

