STUDY DESIGN	
This is a multi-center Phase II randomized study. We plan to enroll 78 patients with biopsy-proven hepatic-limited metastatic colorectal cancer deemed resectable after multi-disciplinary discussion. Eligible patients must have confirmed isolated liver metastases by radiographic imaging of the investigators' choosing. Imaging must include the chest, abdomen, and pelvis regardless of imaging modality chosen. Patients will be randomized to either the control arm or the experimental arm. The control arm will receive mFOLFOX6 every 2 weeks for 4 cycles concurrently with Nivolumab. The experimental arm will first be treated with 2 vaccinations of MVA-BN-CV301 given two weeks apart (Days -28, -14) concurrently with Nivolumab followed by 4 vaccinations of FPV-CV301 given two weeks apart concurrently with mFOLFOX6 and Nivolumab, which will again be administered every 2 weeks for 4 cycles (FPV-CV301, mFOLFOX6 and Nivolumab) After Cycle 4, patients will be re-evaluated for surgical resection by re-staging CT chest, abdomen and pelvis (C/A/P). Patients still considered resectable will undergo surgical resection with the goal of complete resection. Patients who cannot be completely resected will continue to be followed on study, and an additional appropriate candidate will be randomized to the corresponding arm.
 
We will collect peripheral blood and tumor tissue at the time of surgical resection, if applicable, or by re-biopsy if resection is not possible. Post-operative therapy will begin when patients are deemed ready by their surgical oncologist team. Patients in the control arm will then undergo another 8 cycles of mFOLFOX6 with Nivolumab administered concurrently. Nivolumab will then be administered every four weeks. The experimental arm will receive the same post-operative regimen but including FPV-CV301 boosters given concurrently with mFOLFOX6 and Nivolumab. FPV-CV301 will then be administered every 12 weeks, and Nivolumab every 4 weeks. We will collect peripheral blood for evaluation of correlates upon the completion of therapy. The vaccination approach of initial immunization during the neoadjuvant period followed by FPV-CV301 boosters for two years postoperatively was chosen to optimize the induction of a long-lasting tumor-specific host response.

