5.1.2 Neoadjuvant Therapy

Patients who are eligible for and consent to enroll onto this trial will be randomized to either the control arm or the experimental arm. One cycle is 2 weeks.

- Patients in the control arm (Arm A) will receive mFOLFOX6 and Nivolumab given on Day 1 of every 2 week cycle for 4 cycles (Cycle 1 - Cycle 4). The treatment order for Arm A is Nivolumab followed by mFOLFOX6.
- The experimental arm (Arm B) will receive two doses of Nivolumab and MVA-CV301 each given Days -28, -14, followed by four cycles of Nivolumab plus FPV-CV301 given on Day 1 of every 2 week cycle concurrently with mFOLFOX6, which will again be administered every 2 weeks for 4 cycles (Cycle 1 – Cycle 4). For Arm B the order of administration is Nivolumab followed by the vaccination at least one hour prior to mFOLFOX6.

A window of +2 days between administration of Nivolumab +/- vaccination and mFOLFOX6 is allowed. This window will accommodate subjects that receive their chemotherapy locally. If there is more than a 2-day delay for any reason, administration of study drugs should be re-aligned so that the chemotherapy falls within +2 days with the next cycle.

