11.1 Definitions

11.1.1 Adverse Event (AE)

An adverse experience is defined as any unintended or abnormal clinical observation that is not of benefit to the patient whether or not considered related to the study vaccine. Either the condition was not present prior to signature of informed consent, or it has worsened in intensity or frequency following exposure to the study therapy. The following are examples of AEs:

- Unintended or unfavorable sign or symptom
- A disease temporally associated with participation in the protocol

- An intercurrent illness or injury that impairs the well-being of the subject

Hospitalization for elective surgery or routine clinical procedures that are not the result of an AE (e.g., surgical insertion of central line) should not be recorded as an AE.

Disease progression should not be recorded as an AE, unless it is attributable to the study regimen by the site investigator.

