13.2 Rutgers Cancer Institute of New Jersey's Data Safety Monitoring Committee

HCRN will provide the following for review:

- Adverse event summary report
- Audit results if applicable
- Data related to stopping/decision rules described in study design
- Study accrual patterns
- Protocol deviations

The Rutgers Cancer Institute of New Jersey's DSMC will review study data on a quarterly basis. Documentation of DSMC reviews will be provided to sponsor-investigator and HCRN. Issues of immediate concern by the DSMC will be brought to the attention of the sponsor-investigator and other regulatory bodies as appropriate. The sponsor-investigator will work with HCRN to address the DSMC's concerns.

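### Resection status by arm is not on the safety committee's list, and the plan answers excess non-resection only with more enrolment, so an Arm B excess could be absorbed during accrual without safety review

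*Combined protocol and SAP*

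**What the plan says.** Section 3.1 admits only patients with completely resectable disease, and section 1.1 describes resection as the only potentially curative treatment. Under section 5.1.2, Arm B "will receive two doses of Nivolumab and MVA-CV301 each given Days -28, -14, followed by four cycles" with chemotherapy. Arm A starts chemotherapy straight away.

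Section 12.3 expects that "about 5% of the patients will not go on to resection due to either disease progression or complications of neoadjuvant therapy". It sets enrolment accordingly ("We will enroll 74 patients") and continues: "If the number of unresectable patients is higher than 5%, then we will enroll up to 78 patients". The Study Design part of the synopsis keeps an unresected patient in follow-up and says that "an additional appropriate candidate will be randomized to the corresponding arm".

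Section 11.1.1 states: "Disease progression should not be recorded as an AE, unless it is attributable to the study regimen by the site investigator". Section 13.2 gives the DSMC five items for its quarterly review: an adverse event summary, audit results, accrual patterns, protocol deviations, and "Data related to stopping/decision rules described in study design". The only formal stopping rule in section 12 is the efficacy look at 14 deaths (12.8).

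Sections 12.6 and 12.7 restrict efficacy evaluation and the Kaplan-Meier estimates to completely resected patients. Resection rate by arm is not an objective or endpoint in 2.2 or 12.2.2.

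**The concern.** Losing the chance of resection is the earliest serious harm that this design could cause, and the arms differ before surgery in both treatment and timing. In a single patient, progression caused by the regimen or by later chemotherapy looks the same as natural progression, so an investigator has little basis for attributing it. A count by arm is what would separate the two, and the plan asks for none.

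The 5% trigger is a pooled recruitment rule. It does not ask which arm the unresected patients came from or why they were not resected. Same-arm replacement then refills the depleted arm. Because the primary and interim comparisons start at metastasectomy in resected patients, an excess of lost resections would not appear in them either. If the excess were real, patients would go on being randomised while it built up.

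**Working it through.** **1. The plan's own figure.** Inputs from 12.3: 70 resected patients and 5% not resected. 70 / 0.95 = 73.7, which rounds up to 74; 74 × 0.95 = 70.3. The stated enrolment reproduces.

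**2. What the 5% trigger signals.** More than 5% of 74 means at least 4 patients (5% of 74 is 3.7). Taking the stricter reading of 5 or more, and a true rate of 5% in both arms, P(X ≥ 5 | n = 74, p = 0.05) = 0.31. The trigger would often fire by chance and has no by-arm content.

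**3. What the cap can absorb.** 78 − 70 = 8 unresected patients, or 8/78 = 10.3%, before the resected number falls below 70. The documents give no rate by arm, so the splits below are hypothetical. The test is a one-sided Fisher test.

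| Arm B vs Arm A unresected | Rates | p |
|---|---|---|
| 8 of 39 vs 0 of 39 | 20.5% vs 0% | 0.003 |
| 7 of 39 vs 1 of 39 | 17.9% vs 2.6% | 0.028 |
| 6 of 39 vs 2 of 39 | 15.4% vs 5.1% | 0.131 |

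For the first row, p = C(39,8)/C(78,8) = 0.0026. If same-arm replacement held the resected numbers at 35 per arm, the same eight patients would be 8 of 43 versus 0 of 35, and p = C(43,8)/C(78,8) = 0.006. Either way the total stays at 78, and the written response is enrolment only.

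**4. Which lost resections are captured elsewhere.** Section 12.3 names two causes.
- Complications of neoadjuvant therapy: recorded as adverse events regardless of relatedness (11.2.1, 11.2.2), so they reach the DSMC in the event summary.
- Progression: an adverse event only if attributed to the regimen (11.1.1). Unattributed progression is not one, and no other item in 13.2 carries it.

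**5. When a by-arm flag could act.** Assumptions: 37 Arm B patients, uniform accrual over the synopsis's 12 months, and surgery 16 weeks (3.7 months) after start (4 weeks run-in, 8 weeks chemotherapy, about 4 weeks to surgery). The nth outcome is known at month 12n/37 + 3.7.

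| n | Month | Arm B enrolled by then |
|---|---|---|
| 10 | 3.2 + 3.7 = 6.9 | about 21 |
| 20 | 6.5 + 3.7 = 10.2 | about 31 |
| 30 | 9.7 + 3.7 = 13.4 | all (accrual closed at 12) |

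A look at 30 patients comes too late to protect later enrolees, so only the looks at 10 and 20 count.

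**6. Operating characteristics of a flag at 3 of 10 or 4 of 20.** With X the count in the first ten and Y the count in the next ten, P(flag) = P(X ≥ 3) + Σ P(X = x)·P(Y ≥ 4 − x) for x = 0, 1, 2. At p = 0.05 this is 0.0115 + 0.0107 = 0.022.

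| True Arm B rate | First look | Both looks |
|---|---|---|
| 5% | 1.2% | 2.2% |
| 7.5% | 3.4% | 7.2% |
| 10% | 7.0% | 15.3% |
| 15% | 18.0% | 37.8% |
| 20% | 32.2% | 61.0% |
| 25% | 47.4% | 78.9% |

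**The case against.** A reader might infer that loss of resectability is not reportable at all. The documents do not support that: complications are recorded whatever their cause, and attributed progression is an adverse event. Only unattributed progression falls outside.

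A reader might also infer that the harm would never be seen. That too goes beyond the text. Response is assessed before surgery (section 7, footnote 6), response rates are compared by arm, unresected patients stay in follow-up, and 3-year overall survival from registration is a secondary objective (2.2). These could reveal an excess, but late: 13.2 does not send pre-surgery response by arm to the DSMC. No population is named for survival from registration, and 12.6 limits efficacy evaluation to resected patients.

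Same-arm replacement means that somebody must count non-resection by arm to run the trial. That stands, but it is an enrolment mechanism with no review attached. The committee also works under the lead institution's monitoring plan (13.1), which is not among the documents, so what it tabulates beyond the 13.2 list cannot be judged here. Nothing in the documents shows that the run-in raises non-resection.

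Finally, a flag counting everyone not resected by a planned date would add delays, refusals and incomplete resections. That is not the event behind the plan's 5%, and section 5.1.3 fixes no surgery date. This objection is right, and the flag below is limited accordingly.

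**Conclusion.** The gap is real but narrower than a failure of safety reporting. During accrual, loss of resection through unattributed progression is neither an adverse event nor a listed DSMC item. The only stated trial-level responses are enrolment up to 78 and same-arm replacement. An Arm B excess as large as 8 versus 0 of 39 could be absorbed without prompting a safety review. The split is illustrative; the plan supplies only a pooled 5%.

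The by-arm table closes most of the gap and rests on no assumption about rates. The flag's figures assume independent patients, uniform 12-month accrual and the same event definition as the 5%. On those terms it is useful for large excesses (61% at a true 20%) and weak for moderate ones (38% at 15%). This is a cheap improvement to monitoring, not a correction of any figure in the plan.

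**What to change.** In 13.2, add to the quarterly DSMC report, by arm: the number who have reached post-neoadjuvant restaging, the number completely resected, and the number not resected with the reason (progression, complication, other).

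Optionally, in 12.3, add a non-binding flag: the DSMC reviews the by-arm data if 3 of the first 10 or 4 of the first 20 Arm B patients, in order of randomisation, are not resected because of progression or neoadjuvant complications. The review should be called when the flag is reached. Waiting up to three months for a quarterly meeting after month 10.2 could run past the close of accrual.

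The cost is one table in an existing report and a small chance of an unneeded review: about 2% if the true rate is 5%, and about 7% or 15% if it is 7.5% or 10%. The flag uses no alpha, because it gives no route to an efficacy claim, and it prescribes no action for any individual patient.
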